### 7.2 *Sample:*

288 patients with tear film dysfunction, classified as mild to moderate, will be included and randomized into 3 groups; the first being treated with PRO-087 ophthalmic solution, the second with Systane® Ultra ophthalmic solution, and the third with ophthalmic solution Systane® Ultra preservative free.

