### 7.3 *Blinding:*

The double-blind study is a procedure in which the patient and the treating doctor ignore to which intervention group the study patient was assigned. To achieve the blinding of both the drug in research and both comparator drugs, these will be labeled in the same way (masking). Besides the figure of an unblinded pharmacist, who is responsible for the delivery of the medication to the patient, will be added. Blinding codes are protected by an outsider appointed by the study sponsor. The codes are also available in the research center (fully sealed), so that they can be consulted by the investigator in case a subject presents a serious adverse event, prior authorization from the study sponsor; the blinding also continues rigorous during the data analysis and interpretation.

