### 12.1 Inclusion Criteria

---

- ❖  $\geq 18$  to  $\leq 90$  years old
- ❖ Both sexes
- ❖ Mild to moderate tear film dysfunction clinical diagnose
- ❖ Mild to moderate clinical stage of the disease
  - TBUT  $> 5$  sec. and  $< 10$  sec.
  - Schirmer:  $> 4$  mm and  $< 14$  mm
  - OSDI  $< 30$  points
  - Corneal staining  $<$  grade III on the Oxford scale
- ❖ Availability to go to each revision when indicated.

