### 13.3 Schirmer

The sample size was calculated according to the formula for continuous quantitative variables:

With a statistical confidence level of 95%, which corresponds to the error type I, and is equal to 1.96, with a potency of 80% corresponding to the error type II, and is equal to 0.84, a standard deviation for the 1.72 mm/5 min increase in the Schirmer test, with an expected difference of at least 0.13 mm/5 min, was considered.

Based on the above, the result was 80 patients, which increased 20% in consideration of the losses, with a total of 96 patients per group, with total study population of 288 subjects (576 eyes).

Based on the above calculations and considering the primary outcome variable, and Schirmer test used in the study to demonstrate efficacy between the 3 groups, the total population to evaluate will be of 288 subjects.

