#### 14.1.2 Efficacy Assessment Parameters

Parameters	Value
Best-corrected visual acuity	Increase of 1 line in the Snellen chart or 1 logarithmic point (logMAR)
Corneal depithelization	Percentage of the damaged epithelium of the ocular surface, reduction of staining according to the oxford scale.
Tear film break-up time	Increase in the residence of the teal film, measured in seconds. Increase of 30% from baseline or equal or more than 10 sec.
Schirmer test	Increase of more than 30%
Adverse events	Presence of adverse events modifying some of the abovementioned criteria or others, evaluated as serious.
OSDI	Reduction of 20% of the total score from the baseline score.
Goblet cells population	Increase of 20% from baseline

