## 15. Proposed statistical analysis.

---

The statistical analysis will be performed by an investigator blinded to the intervention groups.

The continuous quantitative variables will be presented by measures of central tendency and dispersion (mean, standard deviation and ranges). Nominal and ordinal qualitative variables will be introduced by means of frequencies and ratios.

The Kolmogorov-Smirnov test will be performed to know the normal or abnormal distribution of the results obtained in each study group.

Assuming there is a normal distribution of data, the intra-group differences will be determined by an ANOVA test for repeated measures, with the Pearson correlation coefficient, for the quantitative variables.

For qualitative variables the  $\chi^2$  (chi square) test will be used and in case the expected frequencies are less than 5 the Fisher's exact test will be used.

The differences between groups will be analyzed using the ANOVA test for variance analysis, with the Pearson correlation coefficient, for the qualitative variables.

For qualitative variables, contingency tables 2x2 will be used and the differences will be calculated with  $\chi^2$  (chi square) with Yates's correction and in case the expected frequencies are less than 5 the Fisher's exact test will be used.

The significance level will be of a 0.05 alpha value or less.

The final statistical analysis will include all the subjects that complete the visits listed in the activity chronogram.

Also, those who have been assigned with a treatment (intervention) and attend at least to 1 visit after the baseline will be included and analyzed until the moment they attended.

Those who do not attend at least 1 follow up visit will be excluded.

Those who do not complete the visits will be classified as population with intention to treat.

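### Section 15 assigns the between-group ANOVA to the wrong type of variable; read as intended, it still ignores baseline and gives three arms only 2x2 tables

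*Combined protocol and SAP*

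**What the plan says.** Section 15 limits repeated-measures ANOVA to differences within a group. For differences between groups it says: "The differences between groups will be analyzed using the ANOVA test for variance analysis, with the Pearson correlation coefficient, for the qualitative variables". It then returns to qualitative variables, for which "contingency tables 2x2 will be used and the differences will be calculated" by chi-square with Yates's correction, or by Fisher's exact test when expected counts are small. On error it adds only: "The significance level will be of a 0.05 alpha value or less". It names no baseline covariate, no choice between change and final value, no unit of analysis and no rule for pairwise tests.

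The relevant design facts lie elsewhere:
- **Arms.** Section 7.2: patients "will be included and randomized into 3 groups".
- **Eyes.** Section 6 has both eyes treated. Section 13.3 counts 288 subjects and 576 eyes.
- **Baseline.** Section 9 schedules Schirmer, TBUT, OSDI and impression cytology at baseline. Section 14.1.2 defines TBUT success as "Increase of 30% from baseline or equal or more than 10 sec", and judges OSDI and goblet cells against baseline too.
- **Retention.** Section 15 keeps anyone with at least one post-baseline visit, analysed up to the last visit attended.

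**The concern.** Two consecutive sentences give qualitative variables two different between-group tests and leave quantitative variables with none. The Section 5.1 objective compares PRO-087 with two comparators, and Section 13.3 sizes the trial on Schirmer, so the missing test is the one that matters most. 'Quantitative' is almost certainly meant.

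With the word corrected, two features still fit the design poorly. The ANOVA makes no stated use of baseline, which costs precision if the baseline value predicts the final one. A 2x2 table holds two arms, so a three-arm comparison of responders becomes a set of pairs, and the plan does not say which.

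The unit of analysis and the pairwise rule are also unstated. These are missing details rather than shown errors, but the false-positive rate depends on both.

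**Working it through.** **Plan figures.** Section 15 gives no number to reproduce for this point. I use 80 analysable subjects per arm from Section 13.3, where 80 × 1.20 = 96 and 3 × 96 = 288 agree with the text. The 80 itself does not follow from that section's SD of 1.72 mm and difference of 0.13 mm: 2 × (2.80 × 1.72 / 0.13)² ≈ 2,745 per group. That is a separate Section 13 problem. It affects only the power figures under the fix, not the error rates here.

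**Baseline.** Let r be the baseline–final correlation and k = baseline SD / final SD. The documents give neither, so both are assumed. The entry limits in Section 12.1 make k below 1 plausible. In units of the final-value variance:
- final value: 1
- change: 1 + k² − 2rk
- ANCOVA: 1 − r²

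ANCOVA variance relative to the better of the other two is (1 − r²) / min(1, 1 + k² − 2rk):

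| k | r = 0.3 | r = 0.5 | r = 0.7 |
|---|---|---|---|
| 1.0 | 0.91 | 0.75 | 0.85 |
| 0.7 | 0.91 | 0.95 | 1.00 |
| 0.5 | 0.96 | 1.00 | 0.93 |

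Example, k = 0.7 and r = 0.5: change variance is 1 + 0.49 − 0.70 = 0.79, and 0.75 / 0.79 = 0.95. The reduction runs from 0 to 25%. Randomisation keeps the unadjusted test unbiased throughout.

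**Unit.** With inter-eye correlation ρ (assumed), the mean of 2n eyes has variance σ²(1 + ρ)/(2n), but a pooled analysis assumes σ²/(2n). For three arms in large samples, the ANOVA test at 5% then has true size 0.05^(1/(1 + ρ)):

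| ρ | Formula | Simulation, 80 per arm |
|---|---|---|
| 0.5 | 13.6% | 13.5% |
| 0.7 | 17.2% | 17.1% |
| 0.9 | 20.7% | 20.8% |

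With subject means the simulated size is 4.9–5.0%. OSDI has one score per subject and is unaffected.

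**Pairwise tests, one continuous endpoint, no true differences (simulation, 80 per arm).**
- Three-arm F test alone: 5.0%.
- Ungated at 0.05: 9.0% for the two PRO-087 contrasts, 12.1% for all three pairs.
- Only after a significant F test: 4.1% and 5.0%.

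**Binary responders, one value per subject (exact enumeration, response 5–50%, 80 or 96 per arm).**
- One Yates/Fisher 2x2 table: 1.6–3.6%.
- Either of two tables: 3.0–6.6%.
- Any of three tables: 4.2–9.1%.
- One 2x3 chi-square test: 4.6–5.2%.

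**The case against.** The strongest reply is that a sensible analyst would produce a valid analysis from this text. Much of that stands.

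- **The inflated error rates belong to analyses the plan does not describe.** A reader might infer that Section 15 lets type I error reach 14–21%, or 9–12%. The documents do not support that. The section writes one ANOVA and no pairwise test for continuous endpoints, and never says that eyes are pooled. Section 13 sizes in patients, Section 14.1 counts subjects and Section 15 speaks of subjects. The open point is only that the text does not exclude the other readings.
- **Baseline.** A reader might infer that leaving baseline out biases the comparison. It does not. Sections 13 and 14.1.2 point to change as the outcome, and ANOVA on change is valid. The case for ANCOVA is that it loses no material precision and may gain some.
- **2x2 tables.** They are not invalid. They suit the yes/no criteria in Section 14.1.2 and the two PRO-087 contrasts, where the error for either of two is near nominal. What they cannot do is compare three arms at once. The section's other chi-square sentence is not confined to 2x2 tables, but it follows the within-group test.
- **Consequence.** Section 14.1 judges effectiveness by a threshold within the PRO-087 arm, not by a between-group p-value. That narrows what depends on these tests, though the main objective remains comparative.
- **Blinding.** Section 7.3 says "the blinding also continues rigorous during the data analysis and interpretation". This limits a data-driven choice but does not tell the analyst which test to run.

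The wording error and the lack of any stated three-arm test for responders survive all of this.

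**Conclusion.** The point holds in limited form. As written, Section 15 gives quantitative endpoints no between-group test. With the word corrected, it omits a baseline value that is already collected and offers three arms only two-arm tables.

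The baseline gain is 0–25% of variance over r = 0.3–0.7 and k = 0.5–1, all assumed, so it may be nil. Stating the subject as unit confirms the likelier reading and closes off pooling of eyes, which would give about 14–21% at assumed inter-eye correlations of 0.5–0.9. The pairwise rule is a genuine choice that depends on how success is defined. Without one, the two PRO-087 contrasts on a continuous endpoint give about 9%. Multiplicity across endpoints is not part of this point.

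**What to change.** Change 'qualitative' to 'quantitative' and replace the between-group text with:

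> Quantitative endpoints are compared between the three groups by ANCOVA with the baseline value as covariate, one value per subject (mean of the two eyes; OSDI: the single score). Binary responders are compared, one value per subject, in one 2x3 test, and 2x2 tables are used only for the PRO-087 contrasts with each comparator.

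Three matters need a sentence each:
- **Missing day 90.** A day-90-only ANCOVA would drop subjects whom Section 15 keeps. A repeated-measures model with baseline as covariate is one way to retain them. For Schirmer, first reconcile Section 9, which schedules the test at day 30, with Section 11.3, which omits it. Cytology has only one post-baseline time, so it needs its own missing-data statement.
- **Responder rule.** State how two eyes make one responder. Section 14.1 points to both eyes meeting the criterion.
- **Pairwise rule.** The sponsor should define success and then choose. If beating either comparator counts, use a gate on the three-arm test or Holm over the two contrasts. If both must be beaten, no adjustment is needed.

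The change is SAP wording and standard software, with no new data. Error control has a price. At 80 per arm and SD 1.72 mm, the Schirmer difference with 80% power is 2.80 × 1.72 × √(2/80) = 0.76 mm. At that difference a gate lowers the power of one contrast to 75% if the other comparator equals either arm, or 69% if it lies midway. Holm's stricter step needs (2.24 + 0.84) × 1.72 × √(2/80) = 0.84 mm. These costs mean little beside Section 13.3's own 0.13 mm, for which power is only about 7–8% even without a gate.

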### 5.1 *MAIN OBJECTIVE:*

**To evaluate the effectiveness of preservative-free ophthalmic formulation PRO-087 (by Laboratorios Sophia, S.A. de C.V.) to restore the anatomical and physiological characteristics of the ocular surface, as well as its distribution and the characteristics of the mild to moderate tear film dysfunction syndrome compared to Systane® Ultra and Ultra Systane® preservative free (by Laboratorios Alcon, S.A. de C.V.).**

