## 13. Sample size determination

---

The sample size was calculated according to the 3 major safety variables. The variable is considered the largest number of subjects obtained as the sample size required to meet the objectives of the study.

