### 14.1 Efficacy Evaluation

The variables of the study drug PRO-087 tolerability will be evaluated in the visits indicated in the schedule, using the following parameters:

1. Best-corrected visual acuity
2. Corneal depithelization
3. Tear film break-up time

4. Schirmer test

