5. OSDI
6. Goblet cells population

It is considered that the drug in evaluation PRO-087 is effective for use in patients diagnosed with mild to moderate tear film dysfunction, if they exhibit the changes marked in parameters (14.1.2) by more than 5% of subjects in both eyes, in compliance with all visits and adherence to treatment at an 80% during the time of study assessment.

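### The primary endpoint is not clearly designated, and six unranked efficacy variables are tested at 0.05 with no multiplicity rule

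*Combined protocol and SAP*

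**What the plan says.** - **Objective (section 5.1).** The aim is "to restore the anatomical and physiological characteristics of the ocular surface", compared with two Systane Ultra products. No variable, visit or success criterion is attached.
- **Sample size (sections 13 and 13.3).** Section 13 opens with "The sample size was calculated according to the 3 major safety variables" and then sizes on TBUT, OSDI and Schirmer. Section 13.3 fixes the total at 288 by "considering the primary outcome variable, and Schirmer test used in the study to demonstrate efficacy between the 3 groups".
- **Efficacy variables (section 14.1).** The list runs from "1. Best-corrected visual acuity" to "6. Goblet cells population", with corneal staining, TBUT, Schirmer and OSDI between them. None is ranked. The section then gives its own effectiveness rule: more than 5% of subjects must show the changes tabulated in 14.1.2 in both eyes, subject to visit compliance and 80% adherence. The rule uses no p-value and no comparator.
- **Analysis (section 15).** Between-group differences go to ANOVA. The text attaches this to qualitative variables, but the next sentence gives those a separate method, so I read it as meant for quantitative ones. Qualitative variables go to 2x2 tables with chi-square or Fisher's exact test. The threshold is "The significance level will be of a 0.05 alpha value or less".
- **Schedule (section 9).** Five of the six variables are measured at four post-baseline visits. Goblet cells are measured after baseline only at day 90.

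**The concern.** A comparative efficacy claim needs one designated test, or a rule for combining several. Here the only mention of a primary outcome is a clause in the sample size section. It can mean that Schirmer is the primary variable, or that Schirmer stands beside a primary variable that is never named. Section 13 also calls the same three variables safety variables.

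With six variables, two comparators and no designated visit, the result that is put forward as efficacy could be chosen after the data are seen. Section 15 blinds the analyst to the groups, but that does not prevent a choice among variables. The 5% level would then apply to each test and not to the claim. Section 16 sends the results to the authorities and to publication, so the error rate of the claim matters.

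**Working it through.** **The plan's own figures.** The documents state no family-wise error rate. The per-test level is two-sided 0.05, since section 13.3 says "With a statistical confidence level of 95%, which corresponds to the error type I, and is equal to 1.96", and power is 80%, "with a potency of 80% corresponding to the error type II, and is equal to 0.84". The last step to the total follows: 80 × 1.2 = 96 per group, and 96 × 3 = 288.

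**Inputs for the error rate.** Six efficacy variables (14.1); three groups of equal size (7.2, 7.5, 13.3); 0.05 per test (15). The correlation between variables is not given, so I assume values from 0 to 0.9. All calculations are under no true difference, with large-sample tests at one visit, and treat all six variables alike.

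**Case A: Schirmer is the sole primary.**
- One three-group ANOVA: 5%.
- Two unadjusted contrasts, PRO-087 against each comparator. They share the PRO-087 arm, so their test statistics correlate at 0.5. The chance that at least one exceeds 1.96 in absolute value is 9.1%.

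**Case B: any of six variables counts, one overall ANOVA each.** If the variables are independent, 1 − 0.95^6 = 26.5%. Simulation gives the correlated cases in the table.

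**Case C: any of six variables counts, two contrasts each.** Twelve fully independent tests would give 1 − 0.95^12 = 46.0%. Allowing for the shared arm, independent variables give 1 − (1 − 0.0907)^6 = 43.5%.

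**Case D: as C, counting only false results in favour of PRO-087.** One variable with two contrasts gives 4.5%. Six independent variables give 1 − (1 − 0.0454)^6 = 24.3%.

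| Correlation between variables | B: six ANOVAs | C: twelve contrasts | D: favouring PRO-087 only |
|---|---|---|---|
| 0 | 26.5% | 43.5% | 24.3% |
| 0.5 | 21% | 35% | 18% |
| 0.8 | 14% | 24% | 12% |
| 0.9 | 11% | 19% | 9.5% |

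**Cost of a stricter first step.** Testing at 0.025 in place of 0.05 changes the detectable difference by (2.241 + 0.842)/(1.960 + 0.842) = 1.10. Holding power by sample size instead needs 1.10² = 1.21 times the patients.

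**The case against.** The strongest reply is that section 13.3 does name a primary. It ties the primary outcome variable and the Schirmer test to efficacy across the three groups and fixes the total from Schirmer. On that reading the error is 5% or about 9%, and the other variables are supportive. This reading is reasonable, and the fix adopts it. It does not close the gap, because sections 5, 14 and 15 never repeat the designation, no visit is attached, and two unadjusted contrasts would still exceed 5%.

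A second reply is that section 15 does not plan twelve comparator tests. This stands. For quantitative variables it plans one three-group ANOVA each; only the 2x2 tables imply separate comparisons. Case B is therefore closer to the text and case C is an upper case. However, a significant overall ANOVA does not say which product differs, and no procedure is named for that step.

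A third reply is that the variables overlap. Section 10.3.8 says that the Oxford grade correlates with OSDI and Schirmer, so correlations near zero are unlikely for all pairs. This also stands, and it is why the table runs to 0.9.

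A reader might infer that the plan tests every variable against each comparator at 0.05 and so carries a 35–44% error rate. The documents do not support that. The figure needs the twelve contrasts and correlations of 0.5 or less, and it counts false results that favour the comparator. A reader might also infer that testing at four visits raises the rate by a known amount. Section 15 defines no between-group test by visit; its repeated-measures ANOVA is for change within a group.

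**Conclusion.** The point holds as a defect of designation. The primary variable is ambiguous in section 13.3 and missing from sections 5, 14 and 15. No primary visit, multiplicity rule or pairwise procedure is given. As written, the plan does not secure a 5% error rate for a claim that PRO-087 differs from a comparator.

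The size depends on how the gap is filled. It is 5% or about 9% if Schirmer is the sole primary. If any significant variable may support a claim, it is about 11–27% with one ANOVA per variable and about 19–44% with two contrasts per variable, or 10–24% counting only results in favour of PRO-087. The ranges rest on assumed correlations of 0.9 down to 0 and a single visit.

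It would go too far to say that the plan states that any significant test is proof of efficacy. Its written effectiveness rule in section 14.1 uses no significance test, and nothing says how p-values lead to a claim. The rates for unranked variables are therefore conditional. The gap should be closed before the data are unblinded.

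**What to change.** - State in sections 5, 14 and 15 that Schirmer change from baseline at day 90 is the single primary variable. It is the variable that sets the total in section 13.3.
- Compare PRO-087 with each comparator using Holm or Hochberg at an overall two-sided 0.05, and name this as the pairwise procedure.
- Label TBUT, OSDI, corneal staining, best-corrected visual acuity and goblet cells as secondary. Report them as estimates with 95% confidence intervals and make no confirmatory claim from them.
- Say how this comparison relates to the responder rule in section 14.1, and which of the two decides efficacy.

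The change is to wording only, with no new data or visits. The strictest step is at 0.025, so at the planned size the detectable difference rises by about 10%; keeping the same power would take about 21% more patients. Separately, the Schirmer sample size does not follow from its own inputs: 2 × (2.80 × 1.72/0.13)² is about 2,745 per group, against 80 stated. That needs its own correction, and naming Schirmer as primary does not resolve it.

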#### 14.2.1 Tolerability Parameters

Parameters	Value
Burning	It should be recorded as absent on 95% of the evaluated subjects
Foreign body sensation	It should be recorded as absent on 95% of the evaluated subjects
Tearing	It should be recorded as absent on 95% of the evaluated subjects
Secretion	It should be recorded as absent on 95% of the evaluated subjects
Conjunctival hyperemia	
The following must be accomplished:
 
 
• Absent: <math>\geq 95.0\%</math>
 
• Mild: <math>\leq 5.0\%</math>
 
• Moderate: <math>\leq 2.5\%</math>
 
• Serious: <math>\leq 1.0\%</math>
 

Photophobia	
The following must be accomplished:
 
 
• Absent: <math>\geq 95.0\%</math>
 
• Mild: <math>\leq 5.0\%</math>
 
• Moderate: <math>\leq 2.5\%</math>
 
• Serious: <math>\leq 1.0\%</math>
 

Safety variables of the study drug PRO-087 will be evaluated in the visits indicated in the schedule, using the following parameters:

1. Best-corrected visual acuity
2. Intraocular pressure
3. Ocular surface
4. Anterior segment exploration
5. Posterior segment exploration
6. Tear film break-up time
7. Schirmer test
8. Corneal depithelization
9. Adverse events

It is considered that the drug in evaluation PRO-087 is tolerable for use in human beings, if there are not changes on the marked parameters (14.3.1) by more than 5% of subjects, in both eyes, in compliance with all visits and adherence to treatment at an  $\geq 80\%$  during the time of study assessment.

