### *17.4 Patient elimination*

The causes for a withdrawal of the study from a patient might be the following:

Subject's decision. The patient who wishes to leave the study for any reason can do so at any time, but the investigator must be informed of this. In all cases, the investigator must try to get in contact with the patient as soon as possible for a final assessment in order to do the following:

Document the patient's decision in clinical notes,

Obtain the reason(s) of the departure and record them in the departure form of the CRF,

Assess the clinical state of the patient,

If necessary, take the appropriate therapeutic measures: management of an adverse event or concomitant disease.

Investigator's decision: Especially if there is an adverse event and if the investigator considers that this might threaten the patient's health, actions will be taken as described on the adverse events section or if there is an important disease that needs the prescription of a drug incompatible with the purpose of the study. It will be reported in clinical notes and a serious adverse events report format will be filled and the Research Ethics Committee, the clinical monitor and Pharmacovigilance of Laboratorios Sophia will be informed of this.

A wrongful inclusion according to the protocol. The decision to keep the patient in the will be taken conjointly by the investigator and the sponsor.

Other reasons (insufficient response, need for another treatment).

In all cases, the available data will be kept for safety analysis (assessable population for intention to treat).

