### *17.6 Treatment compliance*

The study drug administration compliance from the patients will be assessed in the Laboratorios Sophia facilities once the dropper bottles of each patient are returned by the investigator; each bottle will be weighed in an analytical balance and the difference will be obtained regarding the initial weight of the container, all values over 80% will be considered as appropriate compliance to the treatment.

In case the study drug compliance is less than 80%, the obtained results will be considered to be analyzed via the intention to treat, see statistical analysis section.

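### Section 14 judges PRO-087 on full attenders with about 80% adherence while section 15 keeps partial attenders; nothing links the two, and read literally the TBUT safety proportion is diluted

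*Combined protocol and SAP*

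**What the plan says.** Section 14 sets three verdicts on PRO-087, each conditioned on attendance and adherence. The safety paragraph after the table in section 14.2.1 calls the product acceptable "if there are not changes on the marked parameters (14.3.1) by more than 5% of subjects, in both eyes, in compliance with all visits", with adherence of at least 80%. The efficacy (14.1) and tolerability (14.2) verdicts carry the same kind of condition. The table in 14.2.1 uses another base, which is not defined: "It should be recorded as absent on 95% of the evaluated subjects". On timing, the safety paragraph says only: "Safety variables of the study drug PRO-087 will be evaluated in the visits indicated in the schedule".

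Section 15 describes a wider final analysis. It takes completers, and subjects assigned a treatment who "attend at least to 1 visit after the baseline will be included and analyzed until the moment they attended". It then says: "Those who do not attend at least 1 follow up visit will be excluded".

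Intention to treat appears with three meanings:
- Section 15, non-completers: "Those who do not complete the visits will be classified as population with intention to treat".
- Section 17.4, withdrawn subjects: "In all cases, the available data will be kept for safety analysis (assessable population for intention to treat").
- Section 17.6, subjects below 80% compliance: "the obtained results will be considered to be analyzed via the intention to treat, see statistical analysis section".

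Two further rules matter. Section 12.2.3 eliminates a subject whose TBUT is under 5 s at any treatment visit. Section 14.3.1 lists a TBUT fall of more than 20% from baseline as a safety change.

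**The concern.** Intention to treat ordinarily means all randomised subjects, analysed as assigned. Here it labels three groups of subjects who departed from the plan, and section 17.6 sends low compliers to a rule that section 15 does not contain. Section 15 does not mention the section 14 verdicts, and section 14 does not mention the section 15 sets.

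The gap matters most for safety. The verdict compares an observed proportion with a fixed 5% limit. If only full attenders count, subjects eliminated for a low TBUT leave both numerator and denominator, and some of them leave because of the event being counted. The same data then give two proportions, and sometimes two verdicts. With no set named in advance, the choice could be made after the proportions are known.

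**Working it through.** **1. Sets side by side.**
- Section 14 verdicts: every visit attended, about 80% adherence.
- Table in 14.2.1: those evaluated, undefined.
- Section 15: at least one post-baseline visit, used up to the last visit attended; subjects with none are excluded.
- Section 17.4: withdrawn subjects' available data kept for safety.
- All randomised, as assigned: defined nowhere.

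**2. Overlap of elimination and safety event.** A fall of more than 20% from baseline b leaves TBUT below 0.8b. This is certain to be below 5 s when 0.8b ≤ 5, that is b ≤ 5/0.8 = 6.25 s. Section 12.1 admits baselines between 5 and 10 s, so this band lies inside the enrolled range. For an eye with baseline below 6.25 s, every counted fall takes that eye below 5 s. The overlap is partial elsewhere: 8 to 6 s is a 25% fall with no elimination, and 5.5 to 4.9 s is elimination with only an 11% fall.

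**3. How little is needed to change a verdict.** Section 13.3 plans 80 per group, raised to 96 for losses. Four events in 80 completers is 4/80 = 5.0%, which is not above 5%. One more event among the 16 lost gives 5/96 = 5.2%, which is.

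**4. Illustration of size.** The documents give no elimination rate, so these inputs are assumed except where noted:
- Baseline uniform on 5-10 s, between-eye correlation 0.8.
- Change normal with SD 1.1 s (section 13.1), between-visit correlation 0, 0.5 or 0.8, between-eye correlation 0.5 or 0.8.
- Elimination at day 7, 30 or 60 if TBUT is below 5 s in either eye, or in both; no attendance afterwards.
- Event: a fall of more than 20% in both eyes at the same visit, at any attended visit up to and including the elimination visit.

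This gives 3 × 2 × 2 = 12 cells for each true mean change. The wider set is section 15 read with section 17.4. A reversal means at or below 5% in full attenders and above 5% in the wider set.

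| True mean change | Full attenders | Wider set | Cells reversing |
|---|---|---|---|
| 0.5 s loss | 6.8-29.2% | 12.3-36.7% | 0 of 12 |
| None | 2.4-12.8% | 4.8-17.7% | 3 of 12 |
| 0.5 s gain | 0.7-4.6% | 1.5-6.9% | 3 of 12 |
| 1.0 s gain | about 0.1-1.3% | 0.4-2.1% | 0 of 12 |

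The full-attender figure is the lower one in every cell. At a 0.5 s loss, 28-39% of subjects are eliminated if either eye triggers it and 11-19% if both must; 35.5-61.5% of subjects with an observed event fall outside the full-attender set. At no change the three reversals are 3.5% vs 6.4%, 3.9% vs 6.1% and 4.2% vs 8.3%.

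**The case against.** Section 14 carries its own condition, so it can be read as choosing adherent completers for a per-protocol style criterion, with section 15 governing the group comparisons. Two sets for two purposes is not in itself a contradiction. This has force: it would go too far to say that section 14 is silent on its set. But the condition may instead qualify only the subjects counted in the numerator, section 17.4 keeps withdrawn subjects expressly for safety, and no text joins the two sections. If the completer reading is accepted, the dilution follows from it.

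The illustration rests on assumed inputs. Even the 1.1 s is loosely worded in section 13.1 and might describe the increase rather than its SD. The protocol looks for TBUT gains, and at a 1.0 s gain no verdict changes. That stands.

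A reader might infer that the treatment comparisons are biased by a completers-only analysis. The documents do not support this: section 15 includes partial attenders, and the section 14 verdicts concern PRO-087 alone. Nor does the quoted intention-to-treat sentence mean that dropouts are analysed separately; section 15 puts those with a follow-up visit in the final analysis.

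**Conclusion.** The point holds as a defect of definition and cross-reference, with one real statistical consequence. Intention to treat is wrongly defined, section 17.6 refers to a rule that does not exist, and nothing links the section 14 verdicts to the section 15 analysis. On the literal wording, the TBUT safety proportion is diluted by removing subjects eliminated for low TBUT.

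The direction is the same in every cell examined. The size, and whether the verdict changes, depend on the assumed baseline, SD, correlations, eye rule and time point. It would be wrong to infer that the safety verdict will generally reverse: it does so in 3 of 12 cells at no change and at a 0.5 s gain, and in none at a 0.5 s loss or a 1.0 s gain. TBUT is one of nine safety variables listed, and no dilution is shown for the others. This should be fixed before analysis.

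**What to change.** - Section 15: define intention to treat as all randomised subjects analysed as assigned. Make completers with at least 80% adherence a per-protocol sensitivity set.
- Section 14, safety and tolerability: state that the verdicts use all subjects with at least one post-baseline assessment, with data up to and including the elimination visit. Report by arm the number with no follow-up visit.
- Section 14, efficacy: state that the verdict uses the intention-to-treat set, with a rule stated in advance for subjects lacking the deciding visit.
- The sponsor should name in advance the visit and eye rule for each verdict and check the 5% limit against them. This matters: with any-visit counting in both eyes, the illustration breaches 5% in 11 of 12 cells of the wider set even at no true change. The time point and the missing-data rule are left to the sponsor.
- Align sections 14.1, 14.2, 14.2.1, 15, 17.4 and 17.6, and reconcile them with section 12.2.3. No change to the clinical elimination criteria is proposed.

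The cost is wording, with no extra visits or data. The downside is that safety event rates will look higher and response rates may look lower.
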